9.1 Adverse Event definition

An *adverse event* will be defined as:

Any untoward medical occurrence in a clinical trial subject administered a medicinal product that does not necessarily have a causal relationship with that treatment. An AE can therefore be any unfavourable and unintended sign (e.g. an abnormal laboratory finding), symptom, or disease temporally associated with the use of a medicinal product, whether or not considered related to the medicinal product.

Furthermore the definition of an AE includes worsening (in severity and frequency) of pre-existing conditions ("Medical history") before first Investigational Medicinal Product (IMP) administration and abnormalities of procedures (i.e., ECG, X-ray, etc.) or laboratory results which are assessed as "clinically significant". Information on AEs must be evaluated by a physician. Each AE is to be classified by the

Investigator as serious or non-serious. This classification will determine the reporting procedure for the event.

What is not an AE?

- Medical conditions present at the initial study visit that do not worsen in severity or frequency during the study are NOT considered as AEs.

9.2 Serious Adverse Event (SAE)

An AE will be defined as serious if it:

- **results in death**
i.e. Causes or contributes to the death.
- **is life-threatening**
Refers to an AE in which the subject was at risk of death at the time of the AE; it does not refer to an AE that hypothetically might have caused death if more severe.
- **requires in-patient hospitalisation or prolongation of existing hospitalisation**
i.e. The AE requires at least an overnight admission or prolongs a hospitalisation beyond the expected length of stay. Hospital admissions for surgery planned before study entry, for social reasons, for any elective surgery (i.e. plastic surgery) or per protocol or for normal disease management (including treatment adjustment) are NOT to be considered as SAE according to this criterion (ie. if the protocol requires planned hospitalisation).
- **results in persistent or significant disability or incapacity**
i.e. The AE resulted in a substantial disruption of the subject's ability to conduct normal activities.
- **is an important medical event, i.e. is medically significant.**
Medical and scientific judgment should be exercised in deciding whether other situations should be considered serious events/reactions, such as important medical events that might not be immediately life-threatening or result in death or hospitalisation, but might jeopardise the subject or might require intervention to prevent one of the other outcomes listed above.
Any suspected transmission via a medicinal product of an infectious agent is also considered a serious adverse event/reaction.

9.3 Eliciting Adverse Event information

The Investigator is required to report all directly observed AEs and all AEs spontaneously reported by the trial subject using concise medical terminology.

In addition, each trial subject will be questioned about the occurrence of AEs using non-leading questions (eg. "How are you feeling?"), at times specified in the Schedule of assessments (Section 5).

Each AE will be assessed for severity, and causality (see definitions in Section 9.6 and 9.7). In addition, each AE is to be classified by the Investigator as serious or

non-serious (see definition in Section 9.2). This classification will determine the reporting procedure for the event (see Section 9.5).

Information on AEs must be evaluated by a physician. Each AE is to be classified by the Investigator as serious or non-serious. This classification will determine the reporting procedure for the event.

Non-serious adverse events are to be reported on the CRF, which is to be submitted to DNDI as specified in Section 13.2. In the CRF, a given AE will be recorded only one time per subject, and the severity recorded will be the maximum level reached. If several distinct episodes of the same condition occur, their number will be recorded in the CRF.

Serious AEs will be reported both on the AE CRF and the SAE forms.

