[name]
[name]
United Kingdom

The Investigator or his/her delegate should document the date when informed consent was obtained (Screening), screening dates, subject initials, Screening Number, date of eligibility and inclusion in the study (Enrolment), Subject Number (when 'Enrolled' – i.e., received treatment) or reason for not enrolling (Screen Failure) or not being randomised, whenever applicable.

Screening should occur between 2 and 28 days before the intended initiation of treatment: detailed procedures are described in Section 8 (Study Assessments).

All subjects must give written consent (see Sections 8.1 and 16.1 for Informed Consent Procedures) to participate in this trial. Consent for screening evaluations may be obtained using the Information and Consent Form (ICF) for the HMR healthy volunteer panel (see Section 16).

All screened subjects will be allocated a Screening Number.

After successful screening, subjects will be enrolled, and allocated to a cohort in the trial, according to their availability and the scheduled trial dates. Subjects will be assigned Subject Numbers (in the order in which they are admitted to the ward) when they receive their dose ('Enrolled' subjects). Subject numbers in the trial will be as shown in Table 2. In Part 1 only, subject numbers will be allocated to treatment according to a randomization schedule prepared by an independent HMR statistician, using a SAS program. Sufficient subjects will be screened to ensure 12 subjects are enrolled per treatment arm tested.

7. Study treatments

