9.4 Adverse Event reporting period

The adverse events reporting period begins upon subject enrolment in the trial (after signature of the ICF) and ends at the Follow-up Visit.

All AEs that occur during the AE reporting period specified in the protocol must be reported to DNDI, whether or not the event is considered medication related.

In addition, any AE that occurs subsequent to the AE reporting period that the Investigator assesses as possibly related to the investigational medicinal product should also be reported as an AE.

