11.6.5. Adverse events

Throughout the study, all AEs observed by either medical staff or professional collaborators, or reported by the subject spontaneously or in response to a direct non-leading question, will be evaluated by the Investigator and noted in the AE section of the CRF, as described in Section 13.2.

Adverse events will be coded using the version of the Medical Dictionary for Regulatory Activities (MedDRA) current at the time of database lock.

All AEs will be listed.

An AE will be considered as treatment emergent if it appeared after the dosing, or if appeared before dosing and worsened after dosing. In case of missing onset date of AE or missing onset time of AE when it appeared on the dosing day, the AE will be considered as a TEAE.

The number of subjects with at least one TEAE will be tabulated by actual treatment and MedDRA system organ class and preferred term.

For each of the following, the number of AEs and the number of subjects with AEs will be summarised by actual treatment as follows:

- TEAEs, by system organ class and preferred term
- drug-related TEAEs, by system organ class and preferred term

Subjects with more than one TEAE will be counted only once, at the maximum causality, for each system organ class and preferred term. AEs with missing severity and/or causality will be treated as severe and possibly related, respectively.

AEs leading to withdrawal, deaths and serious adverse events will be listed separately (fatal events will be listed separately from non-fatal events).

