14.2 Adverse Events

Adverse events will be coded using the version of the Medical Dictionary for Regulatory Activities (MedDRA) which is current at the time of database lock (version 20.1 or higher).

All adverse events will be listed.

The number of subjects with at least one treatment-emergent adverse event (TEAE) will be tabulated by actual treatment and MedDRA system organ class. A treatment-emergent adverse event is defined as an event emerging during treatment having been absent pre-treatment or having worsened relative to pre-treatment¹.

For each of the following, the number of adverse events and the number of subjects with adverse events will be summarised:

- TEAEs by system organ class and preferred term
- TEAEs by system organ class, preferred term and severity
- Drug-related (“Related” as recorded by the Investigator) TEAEs by system organ class and preferred term

Subjects with more than one TEAE will be counted only once, at the greatest severity or causality, for each system organ class/preferred term. Multiple TEAEs in a subject will be counted once per system organ class and preferred term. Adverse events with missing severity and/or causality will be treated as severe and related, respectively.

Summaries will be sorted by system organ class and decreasing total incidence of preferred term.

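### Recording each non-serious AE once per subject, from consent onward, leaves treatment-emergent status, severity and causality undetermined when the same event occurs both before and after dosing

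*Protocol*

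**What the plan says.** **Recording.** In its paragraph on non-serious events, Protocol 9.3 states that "a given AE will be recorded only one time per subject", and that the severity entered is the highest one reached. The next sentence adds: "If several distinct episodes of the same condition occur, their number will be recorded in the CRF". Nothing asks for a date, severity or causality per episode, or for a new record when an event recurs after dosing.

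**Collection window.** Protocol 9.4: "The adverse events reporting period begins upon subject enrolment in the trial (after signature of the ICF) and ends at the Follow-up Visit". Protocol Section 6 (Enrolment procedures): "Screening should occur between 2 and 28 days before the intended initiation of treatment". Section 16 lets the trial-specific consent be signed before screening or after eligibility is confirmed. The pre-dose window is therefore at most 28 days and may be shorter.

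**Classification.** Protocol 11.6.5: "An AE will be considered as treatment emergent if it appeared after the dosing, or if appeared before dosing and worsened after dosing". SAP 14.2 instead requires that the event was absent before treatment or became worse than it was then.

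**Counting.** SAP 14.2 says that "the number of adverse events and the number of subjects with adverse events will be summarised" for TEAEs, for TEAEs by severity and for drug-related TEAEs. It also counts multiple TEAEs in a subject once per system organ class and preferred term. Shell T_AE1 prints a bracketed number of events beside each subject count. Listing shell L_AE1_PG has one onset, one resolution and one time since last dose per row.

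**The concern.** Both TEAE definitions need to know what happened on each side of the dose. The recording rule keeps one severity, one causality and a total number of episodes for the whole period from consent to follow-up. A subject with a headache after screening and another after dosing yields one row that may not show which episode the severity, causality or onset belongs to.

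AEs are the first-listed secondary endpoint, and comparing safety and tolerability across formulations is the secondary objective. Nervous-system events, headache in particular, were prominent in the first-in-human study, and headache also occurs without drug. With 12 subjects per arm, a single misclassified subject visibly changes an arm's incidence. Protocol 13.2 makes the CRF the source document for most recorded data, so episode details not entered there may not exist elsewhere.

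**Working it through.** The documents state no figure on this point, so there is nothing to reproduce. The check has three parts.

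**1. What one record can recover.** All histories with 0 to 2 pre-dose and 0 to 2 post-dose episodes, each mild, moderate or severe, were reduced to what the record keeps: onset, maximum severity and number of episodes. The first onset was taken as the recorded onset. That is an assumption, because neither document says which episode's onset is entered.

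- *All episodes post-dose:* the record fixes TEAE status, maximum severity and the number of episodes. Nothing is lost for subject-level counts.
- *Pre-dose onset, one episode:* not a TEAE, and unambiguous.
- *Pre-dose onset, maximum moderate, two episodes:* the same record fits no post-dose episode (not a TEAE), one post-dose episode that is no worse (not a TEAE under the worsening rule), or one worse post-dose episode (a TEAE).
- *Pre-dose onset, maximum mild, two episodes:* no worsening is possible, but the number of post-dose episodes could be 0 or 1.

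Under this convention the risk is a missed TEAE. If a site enters the latest onset instead, a moderate pre-dose headache followed by a mild post-dose one becomes a moderate TEAE. The error then runs upward. Causality has the same difficulty: an unrelated pre-dose episode and a related post-dose one share one assessment.

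**2. What the bracketed count can mean.** If it counts records, it nearly equals the number of subjects for each preferred term. If it sums the recorded episode numbers, it is right for records with only post-dose episodes, but includes pre-dose episodes in any mixed record classed as a TEAE. The SAP does not choose between these.

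**3. How many subjects.** Inputs:

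- post-dose headache risk p = 6/47 = 0.128 (Protocol 1.4, emodepside arms of the first-in-human study);
- up to 84 subjects, 12 per arm (Protocol 3.1);
- pre-dose headache risk q, not given in the documents and assumed to be 1% to 12.5%. The upper end equals the first-in-human placebo proportion, 2/16 = 0.125;
- pre- and post-dose episodes assumed independent.

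Expected mixed records = 84 × p × q. Chance of at least one among n subjects = 1 − (1 − pq)^n.

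| q | p × q | Expected in 84 | At least one in 84 | At least one in an arm of 12 |
|---|---|---|---|---|
| 1% | 0.0013 | 0.11 | 10% | 1.5% |
| 5% | 0.0064 | 0.54 | 42% | 7.4% |
| 10% | 0.0128 | 1.07 | 66% | 14% |
| 12.5% | 0.0160 | 1.34 | 74% | 18% |

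One subject in an arm of 12 is 1/12 = 8.3 percentage points. These are ambiguous records for one term; not every one would be misclassified, and other recurrent terms would add to them.

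**The case against.** The case against is substantial, and much of it stands.

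- **The episode is not wholly hidden.** Protocol 9.3 requires the number of episodes. This is right: what is lost is each episode's timing, severity and causality.
- **A recurrence that is no worse is arguably not a TEAE.** Under the SAP wording this is a fair reading even with two separate records. Under Protocol 11.6.5, a separately recorded episode that starts after dosing would qualify. The recording rule is therefore not the only cause, and the remedy must say how recurrences are classed. Post-dose worsening is a TEAE under both definitions and can still be missed.
- **The CRF is not in the documents.** It may hold dates per episode, and the listing shell has frequency and treatment-emergent fields. That is possible, but no text provided calls for dates per episode, and the listing shell has one onset per row.
- **The scope is limited.** The rule concerns non-serious events; serious ones also have a form with onset, duration and severity. Safety is descriptive, with no hypothesis tests, and the pharmacokinetic comparisons are untouched.

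A reader might infer that the event counts are unusable, or that TEAEs are always understated. The documents support neither. Records with only post-dose episodes are sound, and for those a one-line definition settles the count. The direction of error depends on which onset is entered, and summing episodes can inflate the count. Nor can a pre-dose maximum severity enter the TEAE severity table under the first-onset convention: such a record is a TEAE only if the post-dose episode was worse, and the maximum is then post-dose.

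**Conclusion.** The concern holds for one class of record: the same non-serious AE occurring on both sides of the dose. For that class, the rule in Protocol 9.3 discards the information that Protocol 11.6.5 and SAP 14.2 need to assign TEAE status, severity and causality, and the error can go either way. Separately, the meaning of the bracketed count in T_AE1 is undefined for any recurrent event.

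The expected size is small. The estimate of about 0.1 to 1.3 subjects in 84 for headache rests on independence, on an assumed pre-dose risk, on enrolment of all 84, and on a first-in-human rate that pools doses up to 40 mg, whereas this trial gives 5 or 10 mg. It is an illustration of scale, not a forecast. The point merits correction because the change is cheap, one subject matters in an arm of 12, and details not collected may be unrecoverable after database lock.

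**What to change.** 1. **Protocol 9.3 and the CRF completion instructions.** Record each distinct episode as a separate AE with its own start and stop date and time, severity and causality. As a minimum, do so for any episode that starts or worsens after dosing.
2. **SAP 14.2 and shell T_AE1.** State that the bracketed number counts treatment-emergent episode records, with each episode classed by its own onset relative to dosing. This also settles how a recurrence that is no worse than a pre-dose episode is treated. Keep the rule that a subject counts once per preferred term.

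The cost is one changed protocol passage with its amendment, a CRF instruction, a short SAP addition, and a few more AE lines per subject. Subject-level counts do not change where all episodes are post-dose.

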9.4 Adverse Event reporting period

The adverse events reporting period begins upon subject enrolment in the trial (after signature of the ICF) and ends at the Follow-up Visit.

All AEs that occur during the AE reporting period specified in the protocol must be reported to DNDI, whether or not the event is considered medication related.

In addition, any AE that occurs subsequent to the AE reporting period that the Investigator assesses as possibly related to the investigational medicinal product should also be reported as an AE.

9.5 Serious Adverse Event reporting requirements

All serious adverse events (SAE) are to be reported immediately (within 24 hours of awareness of SAE by the Investigator) to the Sponsor Clinical Team (via [contact]), and to DNDI Pharmacovigilance (via [contact]), using the SAE report form. This includes a description of the event, onset date and type, duration, severity, relationship to study drug, outcome, measures taken and all other relevant clinical and laboratory data. The initial report is to be followed by submission of additional information (follow-up SAE form) as it becomes available. Any follow-up reports should be submitted as soon as possible, and if possible within 5 working days.

SAEs should also be reported on the clinical trial AE CRF. It should be noted that the form for reporting of SAE (SAE form) is not the same as the AE section of the CRF. Where the same data are collected, the two forms must be completed in a consistent manner, and the same medical terminology should be used.

In addition to immediately reporting SAEs to DNDI, the Investigator will immediately notify the REC of SAEs that occur during this trial, if applicable, in accordance with the standard operating procedures issued by the Research Ethics Service (RES).

A suspected unexpected serious adverse reaction (SUSAR) is a suspected adverse reaction related to an IMP (as defined in Section 9.7) that is both unexpected and serious.

DNDI is responsible for determining the expectedness of the event, using the reference safety information in the Investigator's Brochure. DNDI will notify the MHRA and the European Medicines Agency (EMA) of all SUSARs, and will be

responsible for ensuring that the REC is notified of SUSARs, if applicable.

- SUSARs that are fatal or life-threatening must be notified to the MHRA/EMA and REC within **7 calendar days** after DNDI becomes aware of the event. Follow-up reports should be provided within another **8 calendar days**.
- Other SUSARs must be reported to the REC and MHRA/EMA within **15 calendar days** after DNDI becomes aware of the event.

9.6 Grading of Adverse Event severity

The Investigator will use the terminology MILD, MODERATE, or SEVERE to describe the maximum severity of the AE. This information will be entered in the AE CRFs. For purposes of consistency, these severity grades are defined as follows. Severity is a clinical determination of the intensity of an AE to describe its maximum severity. Please note the distinction between severity and seriousness of AEs. A severe AE is not necessarily a serious AE.

MILD	Does not interfere with subject's usual functions. The subject is aware of the event or symptom, but the event or symptom is easily tolerated (e.g. no reduction in daily activities is required).
MODERATE	Interferes to some extent with subject's usual functions. The subject experiences sufficient discomfort to interfere with or reduces his or her usual level of activity.
SEVERE	Interferes significantly with subject's usual functions. The subject is unable to carry out usual activities and/or the subject's life is at risk from the event.

9.7 Adverse Event causality assessment

For both serious and non-serious AEs, the Investigator is required to assess if there is a causal relationship between the AE and the study drug, i.e. to determine whether there exists a reasonable possibility that the study drug caused or contributed to the AE. To help Investigators with the decision binary tree in the evaluation of causality, the CIOMS VI group recommends that Investigators be asked to consider the following before reaching a decision:

- Medical history (including presence of risk factors)
- Lack of efficacy/worsening of existing condition
- Study medications
- Other medications (concomitant or previous)
- Withdrawal of study medication, especially following trial discontinuation / end of study medication
- Erroneous treatment with study medication (or concomitant)
- Protocol related procedure

The decision to suspend, resume, or permanently interrupt treatment due to an AE will be left to the clinician in charge.

The following categories for relationship to treatment will be used during AE reporting:

Related There is at least a **reasonable possibility** of a causal relationship between an AE and an IMP. This means that there are **facts (evidence) or arguments** to suggest a causal relationship.

Not related There is no reasonable possibility of causal relationship.

The following categories will be used to document outcome of each AE:

Action taken: None, drug treatment, subject withdrawn, other (specified).

Outcome: Completely recovered; recovered with sequelae; ongoing; death; unknown.

9.8 Exposure in utero

Not applicable for this trial (subjects are all male). Study subjects must use contraceptive method (condoms) from first dose of study drug to 90 days after the dose of study drug.

Should their female partner become pregnant despite this preventive measure, the following instructions must be followed:

All pregnancies started in partners of trial subjects within 90 days after administration of the dose of IMP to the study male healthy subject, should be reported using the Pregnancy form (as per the same process and timelines for SAEs) and consent from the subject's partner sought to follow-up the outcome for the new born (up to the age of 2 years).

This must be done irrespective of whether an AE has occurred. The information submitted should include the anticipated date of delivery.

The investigator will follow the subject's partner until completion of the pregnancy or until pregnancy termination (i.e. induced / spontaneous abortion). The investigator will provide pregnancy outcome information in the Child report form. In the case of a live birth, a paediatrician should assess the infant at the time of birth and submit a Child report, and the new born will be followed up to the age of 2 years.

Pregnancies are not considered to be a SAE.

An SAE should be declared in the case of unfavourable pregnancy outcome (abortion, still birth) or congenital abnormality.

In addition, pregnancies considered related to study treatment by the Investigator (ie. resulting from a drug interaction with a contraceptive medication) are considered as AEs and should be recorded on the AE pages of the CRF.

If this might be considered as an AE and assessed as a serious one, an SAE form is to be completed in addition to these two forms.

